Full Protocol

**Retrospective Analysis of the Use of Biologics for Juvenile Idiopathic
Arthritis Related Uveitis in Abou El Reesh Pediatric Hospital, Cairo
University**

Background and introduction

Juvenile Idiopathic Arthritis (JIA) remains, globally, the most common systemic disorder associated with pediatric uveitis. It accounts for approximately 75% of cases of pediatric anterior uveitis (AU) and affects around 30% of ANA positive JIA patients (regardless their type of arthritis).¹ In a cohort study from the Cairo University Pediatric Hospital, JIA accounted for 39% of all cases of pediatric uveitis (unpublished data).

The uveitis, being asymptomatic, chronic and often severe, leads to complications in a large number of patients. Studies estimate that 28–67% of patients with JIA-associated uveitis develop ocular complications, with 12% developing poor visual outcome. The main causes of poor vision were cataract, band keratopathy and macular edema.²

The only means of improving long term effects of uveitis, is early and aggressive anti-inflammatory treatment.³

The main line of treatment of non-infectious causes of uveitis have been topical and systemic corticosteroids. However, it is well known that their prolonged use often leads to ocular and systemic complications, especially in the pediatric age group.⁴

In 2019, the American College of Rheumatology/Arthritis Foundation recommended that in severe active chronic AU or in the presence of sight-threatening complications, methotrexate (MTX) and a monoclonal antibody TNFi should be administered immediately. This is recommended over MTX as monotherapy. They also recommended that inadequate response to one monoclonal TNFi at standard JIA dose, the dose and or frequency should be increased rather than switching to another monoclonal antibody TNFi.⁵

Immunosuppressive drugs are used as steroid-sparing agents but are not free of complications. They increase the susceptibility of children to infection, may cause organ toxicity, reversible bone marrow suppression and may possibly lead to the development of malignancies.³

Thus, our study aims to analyze the use of biologics in our hospital (Abou el Reesh, Cairo University) for children with JIA in controlling their ocular inflammation, prevention of the development of sight threatening complications and if this outweighs their potential associated side effects.

Patients and methods

Population of study & disease condition

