Retrograde analysis of data of all patients presented to Aboul Reesh uveitis clinic taking biologics from January 2017- January 2020. In our hospital, the rationale for using biologics was a high frequency of sight-threatening, frequent recurrences of uveitis or intolerance to steroids or other immunosuppressive drugs, with severe adverse reactions.

Sample size:

It is expected to review 250 patients files of Aboul Reesh uveitis clinic to find all JIA patients with ocular inflammation treated with biologics.

Inclusion criteria

1. Both genders
2. Age up to 16 years
3. Diagnosed JIA according to rheumatological criteria with ocular affection
 - Any type of arthritis (oligoarticular, polyarticular, systemic onset, ocular JIA)
 - ANA positive or negative
4. Uncontrolled uveitis or frequent relapses

Exclusion criteria:

1. Patients without definitive diagnosis as JIA

2. JIA patients on biologics without ocular affection (for systemic control) or with uveitis controlled without the use of biologics
4. Patients without adequate duration for follow-up (less than 3 months) or lost follow up data
5. Patients without available data prior to the start biologics (to compare control of the uveitis)

Methodology

Data will be obtained from by retrospective analysis of all files of patients with JIA from the Abou El Reesh ophthalmology outpatient clinic.

The patients with ocular inflammation treated by biologics will be further analyzed.

The data analyzed will divided into pre and post biologic treatment:

In both we will document-

-Baseline BCVA (in logMar notation)

- Grading of ocular inflammation

(Anterior chamber and vitreous cells were graded as +0.5, +1, +2, +3 and +4 according to the guidelines of the Standardization of Uveitis Nomenclature Working Group)

- Number of relapses in one year

- Development of sight threatening complication

- Dose and frequency of systemic, regional and topical steroids

- Other interventions required

Treatment parameters to be analyzed include type, duration and dose of biologic agent used, time taken to reach inflammation control, adverse effects, and time taken to develop those adverse effects.

Improvement or worsening of activity of inflammation was assessed according to the Standardization of Uveitis Nomenclature Group's directions (2 step improvement or worsening of cells/flare)

Treatment was determined as efficacious if one of the following was fulfilled:

1. No relapses or decrease in the number of relapses

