2. Decrease in dose of topical or systemic steroids
3. Improvement of BCVA of at least two lines

Statistical analysis plan:

All data will be entered into Excel spreadsheets (Microsoft Corporation, Redmond, WA, USA). All statistical analyses will be performed using IBM SPSS version 22.0 software (IBM Corp., Armonk, NY, USA). Descriptive statistics will be summarized as the mean \pm standard deviation for numerical data, frequencies and percentages for categorical data. The ANOVA -test and Pearson moment correlation will be used to compare the means for the numerical data and to identify correlations between them. Chi-square test will be used to compare categorical data. P-values ≤ 0.05 will be considered statistically significant.

References

- 2) Qian Y, and Nisha R. (2010) Juvenile Idiopathic Arthritis Associated Uveitis. *Curr Opin Ophthalmol.* 21(6): 468–472. doi:10.1097/ICU.0b013e32833eab83

Retrospective Analysis of the Use of Biologics for Juvenile Idiopathic Arthritis Related Uveitis in Abou El Reesh Pediatric Hospital, Cairo University

First version, 1st march 2020

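### Efficacy criterion 2 accepts any fall in systemic steroid with no ocular condition, so a reduction made because the joints improved may be scored as ocular efficacy

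*Combined protocol and SAP*

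**What the plan says.** All references are to the combined protocol and SAP.

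- **Aim** (end of the Background and introduction): to analyse biologics "for children with JIA in controlling their ocular inflammation, prevention of the development of sight threatening complications". The target of efficacy is the eye.
- **Efficacy rule** (Methodology): "Treatment was determined as efficacious if one of the following was fulfilled". Criterion 1 concerns relapses and criterion 3 a gain in BCVA. Criterion 2 is "Decrease in dose of topical or systemic steroids".
- **Eligibility** (Inclusion criteria, item 3): "Any type of arthritis (oligoarticular, polyarticular, systemic onset, ocular JIA"). Item 4 also requires uveitis that is not controlled or keeps relapsing.
- **Exclusion** (Exclusion criteria, item 2): "JIA patients on biologics without ocular affection (for systemic control"), and also children whose uveitis is controlled without a biologic.
- **Data recorded before and after the biologic** (Methodology): "Dose and frequency of systemic, regional and topical steroids", with BCVA, inflammation grade, relapses, complications and other interventions. Neither the steroid indication nor joint activity is listed. The files come "from the Abou El Reesh ophthalmology outpatient clinic".
- **Inflammation change** (Methodology): a Standardization of Uveitis Nomenclature (SUN) change is defined as "2 step improvement or worsening of cells/flare", but it is not one of the three efficacy criteria.

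**The concern.** Criterion 2 is sufficient alone. It sets no minimum fall and no time point, and it does not require the eye to be quiet, or even no worse, at the lower dose. A child with both arthritis and uveitis may receive systemic steroid partly for the joints. If the joints respond to the biologic and the dose is lowered for that reason, the rule as written scores an ocular success whatever the eye does.

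This differs from a dose cut for steroid intolerance. Here the biologic works, but on another organ, so a correction for intolerance would not catch it. At stake is the meaning of the efficacy percentage, which could combine joint response with eye response without the reader being able to tell.

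**Working it through.** **Step 1: follow the rule for one child.** Take a child with polyarticular JIA and relapsing uveitis who is on systemic steroid before the biologic.

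- Inclusion items 3 and 4 admit the child.
- Exclusion item 2 does not remove the child, because there is ocular disease and it is not controlled without a biologic.
- After the biologic the joints improve and systemic steroid is lowered. Inflammation grade, relapse count and BCVA are unchanged.
- Criteria 1 and 3 fail and criterion 2 is met. One criterion is enough, so treatment is efficacious.
- The SUN definition does not block this, because it is not part of the efficacy rule.

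**Step 2: size.** The plan has no figure to reproduce. The 250 in the Sample size section is a count of files to review. All inputs below are assumptions.

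- p = share of children whose eye truly responds (0.5 or 0.7)
- q = share whose systemic steroid is at least partly for joints (0.2 to 0.6)
- t = share of those whose dose is lowered because the joints improve (0.5 to 0.8)

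Joint-driven reduction is taken as independent of ocular response, and true ocular responders are taken to be scored efficacious anyway. Then:

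- Scored rate = p + (1 − p) × q × t
- Inflation = (1 − p) × q × t

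| q | t | q × t | Inflation, p = 0.5 | Inflation, p = 0.7 |
|---|---|---|---|---|
| 0.2 | 0.5 | 0.10 | 5 points | 3 points |
| 0.4 | 0.5 | 0.20 | 10 points | 6 points |
| 0.4 | 0.8 | 0.32 | 16 points | 9.6 points |
| 0.6 | 0.8 | 0.48 | 24 points | 14.4 points |

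At p = 0.5 the scored rate would be 55% to 74%. At p = 0.7 it would be 73% to 84.4%.

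**Step 3: a second set of assumptions.** Let a share s of 0.2 to 0.6 be on systemic steroid beforehand, and let a share r of 0.25 to 0.75 of those have it lowered for any non-ocular reason. Then s × r runs from 0.2 × 0.25 = 0.05 to 0.6 × 0.75 = 0.45. The inflation (1 − p) × s × r is 2.5 to 22.5 points at p = 0.5 and 1.5 to 13.5 points at p = 0.7. The range is similar, and its low end is modest.

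Both calculations lean high. A child without a true ocular response who also meets criterion 1 or 3, or whose topical dose falls, would be scored efficacious anyway, so the systemic part adds nothing for that child.

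**The case against.** The strongest reply is that the premise is inferred. The documents never say that any child takes systemic steroid for arthritis. The Background presents corticosteroids as treatment for uveitis, and the systemic control mentioned in exclusion item 2 is a reason for giving biologics, not steroids. The children also come from a uveitis clinic with uncontrolled or relapsing disease, in whom a taper made without regard to the eye is less likely. This stands as a limit on likelihood and size. It does not close the route, because nothing in the rule ties the fall to the eye.

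A reader might infer four stronger things that the documents do not support:

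- **That the error always favours the biologic.** A joint-driven fall does. But joint disease can also keep the dose up after the eye has responded, so that a genuine responder misses the systemic part of criterion 2.
- **That affected children cannot be found afterwards.** Steroid dose by route, inflammation grade, relapses and BCVA are all recorded. Children who qualify only through a systemic fall can be listed, and that list caps the problem. What is missing is the reason for the fall.
- **That comparisons by arthritis type are distorted.** The Statistical analysis plan names only generic tests and no such comparison.
- **That q × t, up to 48%, is the inflation.** It includes children whose eye truly responded and who are scored correctly.

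It can also be said that ignoring every systemic fall whose indication is mixed or unrecorded would discard genuine ocular steroid-sparing. That is right, and the fix allows for it.

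**Conclusion.** The concern holds in limited form. As written, criterion 2 lets a systemic steroid reduction made for the joints be scored as ocular efficacy, and nothing else in the documents prevents it. The misclassification is possible, not automatic. It needs a child on systemic steroid before the biologic whose dose then falls for the joints. It does not arise through topical steroid or in ocular JIA without joint disease.

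The net inflation is put at about 5 to 24 points if half the eyes respond and 3 to 14 points if 70% do. This rests on the assumed p, q and t, on independence, and on no overlap with the other criteria. It shows what is possible and does not estimate this cohort. The point is worth correcting before the efficacy rate is calculated, with medium confidence in its practical importance.

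**What to change.** 1. Add one extraction item before and after the biologic: the recorded indication for systemic steroid (eye, joints, both, not stated), where the file gives it.
2. Amend the scoring of criterion 2. A systemic fall does not count as ocular efficacy when the recorded indication is joints only. When it is both or not stated, it counts only if the SUN grade already collected is no worse at the lower dose.
3. Report each efficacy criterion separately, and topical and systemic falls separately.
4. Add a sensitivity analysis of the efficacy rate with the systemic part of criterion 2 dropped. This needs no new data. Set beside the rate under the rule as written, it bounds the number of successes that could be joint-driven falls.

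Item 2 is a compromise: a joint-driven fall with a mixed or unrecorded indication and an unchanged eye would still count, which is why item 4 is needed. If eye clinic files rarely hold the indication, the report should say so as a limitation.

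The cost is one extraction column, a short change to the definition, and some files marked not stated. The efficacy percentage will probably be somewhat lower. Only scoring and reporting change, and no child's treatment is affected.

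### Efficacy criterion 2 leaves out regional steroids, which are recorded, and credits a fall in one route whatever happens in the others

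*Combined protocol and SAP*

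**What the plan says.** Under Methodology, the list of items documented both before and after the biologic includes "Dose and frequency of systemic, regional and topical steroids". It also includes "Other interventions required".

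The same section then defines success: "Treatment was determined as efficacious if one of the following was fulfilled". There are three criteria:

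- Criterion 1 concerns relapses and has no steroid condition: "No relapses or decrease in the number of relapses".
- Criterion 2 is the only one about steroid use, and it names two routes: "Decrease in dose of topical or systemic steroids".
- Criterion 3 concerns visual acuity and again has no steroid condition: "Improvement of BCVA of at least two lines".

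Activity of inflammation is assessed separately ("2 step improvement or worsening of cells/flare"), but this assessment is not tied to the three criteria. No sentence withdraws success when a regional steroid is added, when the other named route increases, or when another intervention is needed. The statistical analysis plan gives general descriptive and test methods and does not say how changes across routes are to be combined.

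**The concern.** The extraction list and the success rule do not match. Three routes are recorded, two are used, and those two are joined so that a fall in either is enough. The rule therefore cannot tell a child who needed less steroid from one whose steroid moved from one route to another.

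Criterion 2 is the only one of the three that looks at steroid use, and the Background names complications of prolonged corticosteroids as a central problem in this age group. What is at stake is the meaning of the efficacy label. Some children could be reported as treatment successes solely because drops or systemic doses fell while a regional steroid took their place. Others, whose regional use fell with nothing else rising, would be reported as not having met criterion 2.

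**Working it through.** The plan states no figure for this outcome, so there is none to reproduce. The check is of the logic of the definition.

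**Inputs, all from Methodology.** Three routes are recorded. Criterion 2 names two of them and requires a fall in either. I read the success rule as at least one of the three criteria.

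**Enumeration.** Let each route fall, stay the same or rise, with new use counted as a rise. That gives 3 × 3 × 3 = 27 patterns. Criterion 2 fails only when neither topical nor systemic falls, which is 2 × 2 × 3 = 12 patterns. It is therefore met in 27 − 12 = 15.

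| Topical and systemic | Regional | Patterns | Criterion 2 as written | With the change proposed below |
|---|---|---|---|---|
| At least one falls, neither rises | falls or unchanged | 3 × 2 = 6 | met | met |
| At least one falls, neither rises | rises | 3 × 1 = 3 | met | not met |
| One falls, the other rises | falls or unchanged | 2 × 2 = 4 | met | mixed, shown separately |
| One falls, the other rises | rises | 2 × 1 = 2 | met | not met |
| Both unchanged | falls | 1 | not met | met |
| All remaining | any | 12 − 1 = 11 | not met | not met |

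Of the 15 patterns that meet criterion 2, regional use rises in 3 + 2 = 5. In another 4, topical and systemic move in opposite directions without a regional rise. So 5 + 4 = 9 of the 15 include a rise in some route. One pattern outside the 15 is a fall in regional use alone. With the proposed change, 6 + 1 = 7 patterns are clear successes, or 7 + 4 = 11 if the mixed ones are counted.

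**From criterion 2 to the efficacy label.** A child who meets criterion 1 or criterion 3 keeps the label whatever criterion 2 says. Among children who meet neither, let

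- a = those with a topical or systemic fall and a regional rise (label lost),
- b = those whose only steroid change is a regional fall (label gained),
- m = those in the mixed category without a regional rise.

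With n children analysed, the efficacy rate changes by (b − a)/n if mixed cases count as successes, and by (b − a − m)/n if they do not. The documents give none of a, b, m or n. The 250 in the sample size section is a number of files to be searched, not the number of children analysed.

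**The case against.** Several points can be made for the plan, and part of each stands.

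*Most route-switchers may keep their label anyway.* This is correct for any who also have fewer relapses or a two-line gain in acuity. A reader might infer that every child who switches route is misclassified. The text does not support that: the efficacy label is wrong only where it rests on criterion 2 alone.

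*The bias need not be upward.* This also stands. Crediting route shifts raises the rate, and ignoring a regional-only fall lowers it. The documents do not show which is larger.

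*The size is unknown.* A reader might assume that 5–20% of children receive a regional steroid or a rise in another route after starting, and conclude that the rate is overstated by up to 5–20 points. That only returns the assumption as a ceiling on the criterion 2 rate. The ceiling is reached only if every such child also had a topical or systemic fall. It would also wrongly include children whose regional use was unchanged or reduced. Nor does the plan define a steroid-sparing rate for biologics to which the figure could apply.

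*Some opposite changes may be real gains.* A large systemic reduction with slightly more drops is not plainly a failure, and the Background cites both ocular and systemic steroid harm. The documents do not settle how to count it. This argues against failing every child with any rise in another route.

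*Route data will be summarised anyway.* Only partly an answer. A summary of each route on its own does not show whether the child whose drops fell is the child whose regional steroid rose, and it leaves the efficacy label unchanged.

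**Conclusion.** The inconsistency is real and lies in the text itself: regional steroids are recorded, but criterion 2 ignores them and credits a fall in one named route regardless of the others. By the stated rule, a child with less topical or systemic steroid and more regional steroid is an efficacy success even if neither relapses nor acuity improved. A child with less regional steroid and no other change gets no credit.

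The effect on the efficacy rate is confined to children who meet neither criterion 1 nor criterion 3. Its net size and sign cannot be derived from the documents. The 5 of 15 and 9 of 15 are counts of logical patterns. A reader might take them as the share of successes that are false, but patterns are not equally frequent among patients, so they cannot be used that way.

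The conclusion rests on two readings: that one criterion means at least one, and that topical and systemic are meant to exclude regional. The extraction list supports the second by naming the three routes separately.

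**What to change.** Reconcile criterion 2 with the extraction list before analysis, so that all three recorded routes enter the classification:

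- A topical or systemic fall accompanied by a new or increased regional steroid does not count as a criterion 2 success.
- A regional decrease without a rise in another route does count.
- Topical and systemic changes in opposite directions, with no regional rise, are tabulated as a separate mixed category, and the efficacy rate is shown with and without them.
- The change from before to after the biologic is reported for each route.

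This concerns only how outcomes are classified in a retrospective review and alters no child's treatment. The cost is a short rewording and a little more analysis on data already extracted. The success rate may change slightly, in either direction.

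### The two-line BCVA criterion counts gains that follow eye surgery as success of the biologic, and the post-treatment value it uses is tied to no visit

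*Combined protocol and SAP*

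**What the plan says.** - **Success rule (Methodology).** The rule is introduced by "Treatment was determined as efficacious if one of the following was fulfilled". The three criteria are "No relapses or decrease in the number of relapses", "Decrease in dose of topical or systemic steroids" and "Improvement of BCVA of at least two lines". Any one is enough.
- **Periods compared (Methodology).** "The data analyzed will divided into pre and post biologic treatment". The list of items recorded in both periods includes "Baseline BCVA (in logMar notation" in brackets. This is the only visual acuity item, and no visit or window is attached to it. The same list records other interventions, but no rule connects them to criterion 3.
- **Causes of poor vision (Background and introduction).** "The main causes of poor vision were cataract, band keratopathy and macular edema".
- **Follow-up (Exclusion criteria).** "Patients without adequate duration for follow-up (less than 3 months" in brackets are excluded. No common length or upper limit is set. The data window is January 2017 to January 2020.
- **Entry (Inclusion criteria).** Entry rests on uveitis that is uncontrolled or relapses often. There is no threshold for vision.
- **Statistical analysis plan.** It adds nothing on the visit, the eye, the chart or the handling of surgery.

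**The concern.** Criterion 3 is sufficient alone, so whatever moves visual acuity by two lines can decide that the biologic worked. Three things other than the drug can affect it.

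1. **Surgery.** Two of the three causes of poor vision that the protocol names, cataract and band keratopathy, can be treated surgically. A child whose relapses and steroid dose are unchanged, but who gains two lines after an operation, is counted as a success of the biologic. The study is a single-group before/after comparison, so no control arm would reveal or offset this.
2. **Choice of visit.** The post-biologic acuity carries the label of a baseline and has no date. Follow-up runs from 3 months to about 3 years (the length of the data window), so two analysts could compute different rates from the same files. If any visit counted, children seen more often would have more chances of a gain by noise.
3. **Room to improve.** Eyes that see well at the start may have little or no room to gain two lines, so the criterion 3 rate depends partly on the mix of starting acuity.

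At stake is the meaning of one of the three routes to the study's efficacy label, and whether that route can be computed reproducibly.

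**Working it through.** The plan gives no figure to reproduce: the 250 files are a screening count, with no expected rate, SD or power. The rules come from the documents. Every numerical input below is an assumption, used only to show scale.

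**Step 1. Surgery, criterion 3 alone.** Let s be the share of patients with vision-restoring eye surgery after starting the biologic (5–30%), and g the share of those who gain two lines (60–80%). It is also assumed that they would not have gained two lines without surgery.

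- Low: s × g = 0.05 × 0.60 = 0.03
- High: s × g = 0.30 × 0.80 = 0.24

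So 3–24% of patients meet criterion 3 through surgery.

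**Step 2. Surgery, overall success.** Because one criterion is enough, surgery changes the result only for patients who would otherwise fail. Let r be the success rate without surgical credit, independent of surgery. The rise is (1 − r) × s × g.

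| r (assumed) | Low | High |
|---|---|---|
| 40% | 0.60 × 0.03 = 1.8 points | 0.60 × 0.24 = 14.4 points |
| 60% | 0.40 × 0.03 = 1.2 points | 0.40 × 0.24 = 9.6 points |
| 80% | 0.20 × 0.03 = 0.6 points | 0.20 × 0.24 = 4.8 points |

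**Step 3. Visit choice, with no true change.** Take one line as 0.1 logMAR, so two lines are 0.2. Let σ be the SD of a single normal reading, with independent errors. For one pre and one post reading, P(gain ≥ 0.2) = 1 − Φ(0.2 / (σ√2)). For the best of k post readings, average 1 − [1 − Φ(x − 0.2/σ)]^k over a standard normal x for the pre reading.

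| σ (logMAR) | One set visit | Best of 4 | Best of 10 |
|---|---|---|---|
| 0.07 | 2.2% | 7% | 13% |
| 0.10 | 7.9% | 21% | 34% |
| 0.12 | 11.9% | 30% | 45% |

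**Step 4. Room to gain.** The required post value is baseline − 0.2. If the best value the chart can record is F, the criterion is out of reach for any baseline better than F + 0.2.

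| Chart limit F (logMAR) | Out of reach if baseline is better than |
|---|---|
| 0.0 | 0.2 |
| −0.1 | 0.1 |
| −0.2 | 0.0 |
| −0.3 | −0.1 |

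The documents do not state the chart, so F is unknown.

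**The case against.** **On surgery.** A reader might infer that 3–24 points of the overall success rate come from surgery. The documents do not support that. Under the any-one-of-three rule, the figure applies to criterion 3; it would apply to overall success only if nobody succeeded by another route (r = 0). The protocol also plans to record other interventions, so what is missing is a rule rather than data. Surgery is not mentioned as such, and its frequency in this cohort is unknown. Nor is all distortion of criterion 3 upward: a cataract that develops after the start can hide a real benefit. These limits stand. They reduce the size of the effect, but they do not change the fact that the rule as written accepts a gain from any cause.

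**On the visit.** A reader might take 13–45% as the expected false-gain rate, or assume that more visits always mean more chances. Both need a best-of-visits or any-visit rule, and the plan states no such rule and no count of 10 visits. One acuity item is listed per period, and with one post reading the range is 2–12%. Best of 10 is therefore a worst case. What stands is that nothing in the text rules it out.

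**On room to gain.** A reader might infer that well-seeing eyes can never meet the criterion and so count as failures. Neither follows. On a chart that reads to −0.3, an eye at 0.0 can still formally qualify, and a patient with good vision can succeed on relapses or steroid dose.

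**On a 3-month value.** The follow-up exclusion sets a length of follow-up. It does not guarantee a visit, or a recorded acuity, at 3 months, so a remedy needs a window and a rule for missing values.

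**Conclusion.** The point holds. That criterion 3 credits gains after eye surgery to the biologic follows directly from the stated success rule. That the post-biologic acuity has no defined visit is equally plain from the text. The plan should be changed on both, and the change is worth making even though the size of the effect is uncertain.

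Under the assumptions above, surgery raises the overall success rate by about 2–14 points if 40% succeed otherwise and 1–10 points if 60% do; the effect shrinks further as r rises. Noise at one set visit gives a false two-line gain in 2–12%, and leaving the visit open allows more.

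The room-to-gain issue is a reporting matter. It lowers the criterion 3 rate by an amount that depends on the chart and on starting acuity, and it does not by itself make any patient a failure on the composite.

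**What to change.** Amend criterion 3 and the statistical analysis plan as follows.

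- **Visit.** Define the post value as the BCVA nearest 3 months after the start of the biologic, within a stated window, and again at 12 months where available. Require a gain of at least 0.2 logMAR.
- **Eye.** State which eye decides for the child.
- **Surgery.** If eye surgery comes before that value, use the last post-biologic BCVA before surgery. If there is none, the patient is not assessable on criterion 3 and is judged on criteria 1 and 2. Report operated eyes separately.
- **Room to gain.** Report the two-line rate among eyes with baseline BCVA of 0.2 logMAR or worse, and mean logMAR change for all eyes.
- **Confirmation.** Use a gain confirmed at the next visit only as a sensitivity analysis in patients who have one. As a main requirement it would bar children with short follow-up from meeting criterion 3.

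The cost is wording, plus surgery and visit dates from files already being read. No new patients or measurements are needed. The BCVA success rate may fall, and some patients will lack a value in the window; their number should be reported.

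### A two-line BCVA gain alone counts as efficacy, with no same-test rule, post-biologic reading time or lower age limit, so a young child's maturation or change of test can be credited to the biologic

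*Combined protocol and SAP*

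**What the plan says.** The Methodology section sets out a within-patient comparison: "The data analyzed will divided into pre and post biologic treatment". Acuity heads the list of items documented in both periods, as "Baseline BCVA (in logMar notation"). No chart or optotype is named, and no time is set for the post-biologic reading.

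The success rule reads "Treatment was determined as efficacious if one of the following was fulfilled". The third item is "Improvement of BCVA of at least two lines", so a child who meets neither of the first two criteria (relapses, steroid dose) is still a success on acuity alone. The size of a line is not stated.

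The Inclusion criteria give age as "Age up to 16 years", with no lower bound. The only rule on length of follow-up is in the Exclusion criteria: "Patients without adequate duration for follow-up (less than 3 months) or lost follow up data". The population is patients "taking biologics from January 2017- January 2020", a three-year window. The Statistical analysis plan names ANOVA, Pearson correlation and chi-square. It describes no comparator and no handling of age or of differing follow-up.

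**The concern.** The second acuity reading is always taken at an older age than the first. In a young child, recorded acuity can improve with no change in the eye disease: vision matures, cooperation improves, and the child may move to a different test. LogMAR standardises the unit of the score, not the test that produced it. With no untreated or age-matched group, nothing in the design shows how much of a two-line gain is of this kind, and the success rule credits all of it to the biologic.

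Three results are exposed: the proportion meeting criterion 3, the before/after comparison of mean BCVA, and, less strongly, the overall percentage called efficacious. If the second reading is taken later in children followed for longer, the age-related gain also runs alongside time on drug, and duration is among the items to be analysed ("Treatment parameters to be analyzed include type, duration and dose of biologic agent used").

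**Working it through.** The plan gives no acuity response rate, SD or maturation rate, so there is no figure of its own to reproduce. What follows is an illustration.

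**Inputs from the documents**
- Threshold: two lines (Methodology, criterion 3).
- Interval t between readings: 3 months is the minimum follow-up (Exclusion criteria). Three years, the length of the data window, is used as an illustrative upper end.

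**Assumed inputs, not in the documents**
- One line = 0.10 logMAR, so two lines = 0.20 logMAR.
- SD of the change between two readings of one eye: s = 0.12 logMAR, varied below from 0.08 to 0.16.
- Age-related gain in a young child: g = 0, 0.03 or 0.06 logMAR per year.
- No drug effect, no disease-related loss and no change of test.

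**Formula.** P(criterion 3 met) = 1 - Phi((0.20 - g × t)/s), for one eye.

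With g = 0: 1 - Phi(0.20/0.12) = 1 - Phi(1.667) = 4.8% at any t. This part is measurement noise.

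With g = 0.06 and t = 3: 1 - Phi((0.20 - 0.18)/0.12) = 1 - Phi(0.167) = 43.4%.

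| g (logMAR/year) | 3 months | 1 year | 2 years | 3 years |
|---|---|---|---|---|
| 0 | 4.8% | 4.8% | 4.8% | 4.8% |
| 0.03 | 5.4% | 7.8% | 12.2% | 18.0% |
| 0.06 | 6.2% | 12.2% | 25.2% | 43.4% |

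**Sensitivity to the SD, 3 months to 3 years**
- s = 0.08: 0.8% to 8.5% (g = 0.03); 1.0% to 40.1% (g = 0.06).
- s = 0.16: 11.4% to 24.6% (g = 0.03); 12.4% to 45.0% (g = 0.06).

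The level moves with s, but the rise with t remains.

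**Change of test.** This is a step, not a slope, and it can go either way. With s = 0.12 and g = 0, an assumed step of 0.10 in the child's favour gives 1 - Phi((0.20 - 0.10)/0.12) = 20.2%. The same step against the child gives 1 - Phi((0.20 + 0.10)/0.12) = 0.6%.

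**Effect on the any-one-of-three result.** Let q be the share already successful on criterion 1 or 2, treated as independent of acuity. The points added by maturation are (1 - q) × (rate - 4.8%).
- At 3 months, q = 0.70: 0.30 × 0.6 = 0.2 (g = 0.03) and 0.30 × 1.4 = 0.4 (g = 0.06).
- At 3 years, q = 0.70: 0.30 × 13.2 = 4.0 and 0.30 × 38.6 = 11.6.
- At 3 years, q = 0.30: 0.70 × 13.2 = 9.2 and 0.70 × 38.6 = 27.0.

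These apply to young children only. The whole-cohort figure shrinks with their share, which the documents do not give.

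**The case against.** The strongest reply is that the direction of the net error is not established. The Background describes chronic, often severe disease, with ocular complications in 28-67% of patients and poor visual outcome in 12%. The Inclusion criteria select uncontrolled or frequently relapsing uveitis. If the biologic did nothing, such eyes might lose acuity, and that loss would work against maturation. In the model above, a loss of 0.03 logMAR per year would cancel a gain of 0.03 exactly and return the rate to 4.8%. This stands: a reader might infer that the plan must overstate efficacy, but the documents support only that it can.

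Second, slope, SD and age mix are all outside assumptions, and the tabulated rates are for one eye on one criterion. A reader might take 43.4% as the share of the cohort wrongly called efficacious. It is not. It needs the steeper slope sustained for the full three years, and it is diluted by children who already meet criterion 1 or 2.

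Third, a reader might infer that the error necessarily grows with time on drug. That needs a post-biologic reading taken later in longer follow-up, and the plan leaves that time open. An early reading at a fixed time would remove the rise. Nor does the Statistical analysis plan name a correlation of biologic duration with BCVA; it mentions correlation only in general terms. Nor can a change of chart be assumed to favour the biologic.

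Fourth, a same-test rule does not remove maturation. This also stands, and is why reporting by age band and a result without criterion-3-only successes are needed as well.

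None of this supplies the missing conditions. The rule as written still lets a non-drug gain decide a child's classification.

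**Conclusion.** The point holds as a weakness in how criterion 3 is defined. The criterion is sufficient alone, the design is uncontrolled, and nothing limits age, test or reading time, so in young children a two-line gain unrelated to the drug can be scored as efficacy.

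The documents do not fix its size. Under the stated assumptions, maturation raises the single-eye criterion 3 rate from 4.8% to between 5.4% and 6.2% at 3 months, and to between 18.0% and 43.4% at 3 years. The later figures apply only if the second reading is that late. The effect is near zero in older children, smaller in the overall efficacious percentage than in criterion 3 itself, and may be offset by disease-related loss. Criteria 1 and 2 are not affected. It is worth correcting because the remedy is cheap and bears on what a criterion 3 success can be taken to mean.

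**What to change.** Before extraction:

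1. Record the child's age and the type of acuity test with every BCVA.
2. Take the post-biologic BCVA in one prespecified time window for all children.
3. Count criterion 3 only when both readings come from the same type of test and the gain is at least 0.20 logMAR. Otherwise score it not evaluable, judge the child on criteria 1 and 2, and report how many children this affects.
4. Report the criterion 3 rate by a prespecified age band at the pre-biologic reading (for example, below and above 6 years).
5. Report the efficacious percentage with and without children who qualify on criterion 3 alone. This also deals with the unevenness that not-evaluable children have two routes to success rather than three.

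Do not adjust the BCVA analysis for the interval between readings. In a one-arm study that interval nearly coincides with time on drug, so adjustment cannot separate maturation from benefit and may remove real benefit.

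The cost is two extraction fields and a few sentences in the analysis plan. The downside is that some children become not evaluable on criterion 3, including any, of whatever age, whose file does not record the test. The efficacious percentage may be lower. In a retrospective file review that number could be appreciable, which is why it should be reported.
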